4.2. Sample Size and Power Considerations

The sample size of 30 evaluable subjects conforms to industry and regulatory standards for determination of irritation when topical application to skin is followed by light exposure.

4.3. Subject Populations for Analysis

All subjects who receive treatment will be evaluable for AEs. The evaluation of phototoxicity potential of the study products will be assessed for all subjects completing the study.

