3.3. Study Population

3.3.1. Subject Population

A sufficient number of subjects will be enrolled in order to provide 30 completed subjects evaluable for analysis; an individual subject will be allowed to participate in the study one time only.

A rationale for the choice of sample size is provided in Section 4.2 of this protocol.

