3.3.3. Interruption or Discontinuation of Treatment

In accordance with legal requirements and ICH-GCP guidelines, every subject or his/her legal representative has the right to refuse further participation in the study at any time and without providing reasons (see also Section 5.3). A subject's participation is to be terminated immediately upon his/her request. The Investigator should seek to obtain the reason and record this on the case report form (CRF).

If at the time of refusal a study product has already been administered, the subject should be advised on follow-up safety investigations.

If a subject develops a serious adverse event (SAE), his/her termination from the study will be considered by the Investigator. Similarly, if the subject develops conditions over the course of the study which would have excluded his/her entry in the study according to the safety-related medical exclusion criteria, he/she must be withdrawn immediately.

The subject may be withdrawn from the study at any time at the discretion of the Investigator for medical reasons and/or due to non-adherence to the treatment scheme and other duties stipulated in the study protocol. The reasons are to be documented on the CRF.

In addition, the Sponsor retains the right to end the study at any time if the study cannot be carried out as agreed upon in the protocol. In case of premature termination or suspension of the study, the Sponsor's study manager will promptly inform the Investigator/institutions and regulatory authorities of the termination or suspension and the reason for that. It is the responsibility of the Principal Investigator (PI) to notify the Institutional Review Board (IRB) in the case of premature termination/suspension.

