3.3.4. Withdrawals

The following medical and other reasons justify a premature termination (by subject or Investigator) of any of the study investigational products (IPs).

- Adverse Event/Serious Adverse Event
- Death
- Protocol Violation (e.g. non-compliance)
- Investigator Judgment
- Pregnancy
- Lost to Follow-up
- Withdrawal by Subject
- Study Terminated by Sponsor
- Other

If a subject withdraws from the study, all efforts will be made to complete a final evaluation, if possible. Subjects discontinued for having experienced an AE will be followed until the AE is resolved, a reasonable explanation is provided for the event, or the subject is referred to his/her own primary medical doctor (PMD). The specific AE in question will be recorded on the appropriate CRF.

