3.6. Adverse Events

3.6.1. Method of Determining Adverse Events

Safety assessments will include recording AEs reported spontaneously by the subject or collected by the Investigator. AEs will be recorded at each visit throughout the study on the appropriate CRF. Every attempt should be made to describe the AE in terms of a diagnosis. If a clear diagnosis has been made, individual signs and symptoms will not be recorded unless they represent atypical or extreme manifestations of the diagnosis, in which case they should be reported as separate events.

Subjects should be asked whether, since the time of the last observation or visit, they had any of the following:

- Experience any changes in well-being;
- Used any new medications;
- Changed medication regimens (both prescription and OTC); and/or
- Were admitted to a hospital or had any accidents.

All questions should be of a general nature and should not suggest symptoms.

When an AE is suspected, all relevant evaluations will be carried out and appropriate treatment provided. Additional follow-up will be done as necessary (Section 3.6.4) and recorded in the subject's source documents, and the results will be provided to the Sponsor.

For AE definitions and reporting requirements refer to Section 3.6.2 and Section 3.6.3.

Note: Any observed response which can be denoted using the irritation criteria summarized in Table 3 and Table 4 will not be considered an AE. Likewise, any tape-related irritation will only be noted as an AE when all patches are discontinued due to tape reaction around all sites (see Section 3.6.6).

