3.6.6. Expected Adverse Events

Any observed response in the patch test area that can be denoted using the irritation criteria summarized in Table 3 and Table 4 will not be considered an AE.

Tape related reactions will only be recorded as AEs when the subject is discontinued due to tape reaction around all sites. When 1 or 2 sites are experiencing severe tape related reactions, the application site will be stopped and the subject will continue on the study.

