4. STATISTICAL METHODS

4.1. General Considerations for Data Analysis

The focus of the statistical analysis will be the comparison with controls of the phototoxic response to the study products. The parameter for phototoxicity will be the mean of Day 3 and 4 scores (sum of erythema and edema).

All statistical processing will be performed using the SAS[®] system (version 9.2 or higher). No interim or subgroup analyses are planned.

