4.6. Safety Evaluation

4.6.1. Local Tolerability Assessment

All assigned scores during the study for subjects who complete the study will be summarized using frequency counts by treatment for Days 2, 3 and 4. Selected pairwise comparisons will be performed on the mean of the Day 3 and Day 4 response scores (sum of erythema and edema

scores) in the context of the analyses of variance (ANOVA). Pairs to be compared are: each study product irradiated versus non-irradiated and all pairwise comparisons on each side (CCP-020 [Diacerein 1%] topical ointment versus vehicle ointment on both the irradiated and non-irradiated sides and CCP-020 [Diacerein 1%] topical ointment versus untreated and vehicle ointment versus untreated on the irradiated side).

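### Phototoxicity is analysed in completers only and scored site reactions are not adverse events, so a subject who reacts and withdraws after irradiation appears in no planned reaction result

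*Combined protocol and SAP*

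**What the plan says.** The analysis population for the main objective is given in Section 4.3: "The evaluation of phototoxicity potential of the study products will be assessed for all subjects completing the study". The synopsis has the same rule. Section 4.6.1 applies it to the descriptive tables for Days 2, 3 and 4: "All assigned scores during the study for subjects who complete the study will be summarized using frequency counts by treatment". The endpoint in Section 4.1 is the Day 3 and Day 4 average of the erythema plus edema score. No rule is given for a subject with only one of those days, although Table 4 has a code for an absent subject.

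Section 3.6.1 states: "Any observed response which can be denoted using the irritation criteria summarized in Table 3 and Table 4 will not be considered an AE". Section 3.6.2.1 repeats this, and Section 3.6.6 restates it for the patch test area. The exclusion has no severity limit. Sections 3.6.1 and 3.6.6 make an exception on discontinuation for tape reactions, but none for reactions to the products.

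Withdrawal is open throughout. Section 3.3.3 says: "The subject may be withdrawn from the study at any time at the discretion of the Investigator for medical reasons". Section 3.3.4 adds: "If a subject withdraws from the study, all efforts will be made to complete a final evaluation, if possible". Enrolment is tied to completion in Section 3.3.1: "A sufficient number of subjects will be enrolled in order to provide 30 completed subjects evaluable for analysis".

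**The concern.** Each rule is ordinary by itself. Together they leave a gap. A subject may react at the irradiated CCP-020 site and leave, or be withdrawn, between the Day 2 irradiation and the Day 4 reading. The Day 3 score and any final evaluation are then collected but used in no planned reaction result. Enrolment aims for 30 completers regardless, so the analysed set can reach its target size without that subject.

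Phototoxic potential is the study's main objective (Section 2). If withdrawal is related to the reaction, the exclusion depends on the outcome and moves the result towards no phototoxic potential. In a safety study that is the unfavourable direction for an error.

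**Working it through.** **The plan's own figure.** The only stated size is 30 evaluable subjects. Section 4.2 justifies it by convention and gives no effect size, standard deviation, error rate or dropout rate, so it cannot be reproduced. The main check is therefore a trace through the planned outputs.

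**Step 1. Where would a withdrawn reactor appear?** Here a reactor is a subject with a scored reaction at the irradiated CCP-020 site.

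| Planned output | Population or rule | Shows the reaction? |
|---|---|---|
| Pairwise ANOVA comparisons (4.3, 4.6.1) | Completers | No |
| Score frequency tables (4.6.1) | Completers | No |
| AE tables (4.3, 4.6.2) | All treated subjects | In the denominator only; a Table 3/4 response is not an AE |
| Listing of deaths and SAEs (4.6.2) | SAEs are defined as a subset of AEs (3.6.2.2) | No, read literally |
| Demographics, compliance, medical history, medications (4.3.1, 4.3.2, 4.4) | Randomized subjects | No score shown |

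Section 4 plans no disposition table, summary of withdrawal reasons, listing of non-completers' scores or retest summary.

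**Step 2. Effect on a reaction rate.** Assume 30 completers score 0 at every site and k further subjects withdraw after Day 3 with a reaction. The rate is k/(30 + k), with exact (Clopper-Pearson) two-sided 95% limits.

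- As planned: 0/30, upper limit 1 − 0.025^(1/30) = 11.6%
- k = 1: 1/31 = 3.2% (0.1% to 16.7%)
- k = 2: 2/32 = 6.3% (0.8% to 20.8%)
- k = 3: 3/33 = 9.1% (1.9% to 24.3%)

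**Step 3. Effect on the mean contrast.** Table 3 allows a sum of 0 to 3 + 2 = 5. Against a site scoring 0, the contrast is 0 under the plan and k × s/(30 + k) if leavers with score s are included. Take s from 2 to 5.

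- k = 1: 2/31 = 0.06 to 5/31 = 0.16
- k = 2: 4/32 = 0.13 to 10/32 = 0.31
- k = 3: 6/33 = 0.18 to 15/33 = 0.45

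**Step 4. A less extreme case.** Let p be the true reactor rate and w the share of reactors who withdraw. The rate among completers is p(1 − w)/(1 − pw), and the chance of seeing at least one reactor among 30 completers is 1 − (1 − rate)^30. With p = 5% assumed:

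- w = 0: 78.5%
- w = 25%: rate 0.0375/0.9875 = 3.8%, chance 68.7%
- w = 50%: rate 0.025/0.975 = 2.6%, chance 54.1%

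With p = 2% the three chances are 45.5%, 36.6% and 26.3%. With p = 10% they are 95.8%, 90.9% and 80.3%.

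**The case against.** The best counter-argument is that this will seldom happen. There is one application and one irradiation, both finished on Day 2, and only two reading visits follow. A subject with a reaction has no further scheduled exposure to avoid, and a final evaluation is sought from anyone who leaves. This is a fair point about likelihood. It does not alter the rule, and the protocol gives no withdrawal rate by which to dismiss it.

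Second, the ANOVA does not decide the conclusion alone. Section 3.5.7.1 requires a reproducible result on retest before phototoxicity is inferred, so a subject who left before retest would be unconfirmed in any case. This stands, and it limits the claim: the harm is an unreported suspected reaction and a biased comparison, not a missed confirmed case.

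Third, other traces exist. The withdrawal reason goes on the CRF, medication for a reaction would be in the by-subject listing, and symptoms outside Tables 3 and 4, such as pain, can still be AEs. None of these shows the site score.

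Fourth, completing the study is not defined, so a subject who leaves but attends a final evaluation might be counted as a completer. Also, Section 3.4.5.2 refers to a SAP still to be finalized, which could add the missing outputs. Both are reasons to write the rule down; neither supplies it here.

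**Conclusion.** The concern holds on the protocol as written. A stated population rule, combined with a stated AE exclusion, drops a withdrawn reactor's collected scores from every planned reaction result, and nothing in Section 4 restores them. The text settles that the gap exists. Its size depends on assumptions about how many reactors withdraw and how they score. Steps 2 and 3 take the extreme case in which every reactor leaves and every completer scores 0; Step 4 shows smaller but still material losses under partial withdrawal. With about 30 subjects, one omitted reactor is enough to turn some reactions into none. The point is worth correcting, but in a four-day study it may affect few subjects or none.

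**What to change.** In Sections 4.3 and 4.6.1:

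- Define the phototoxicity set as all treated and irradiated subjects with at least one post-irradiation score.
- At every site, use the mean of the available Day 3 and Day 4 scores, or the single score if only one exists.
- Put every collected score in the frequency tables.
- Keep the completers analysis as a sensitivity analysis.
- Add a listing of withdrawals by reason with the last score at each site, identifying those due to a Table 3/4 response.

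The cost is protocol and SAP wording, one table and one listing. There is a small loss of precision, because a single-day score has variance 2/(1 + ρ) times that of the two-day mean. For an assumed Day 3/Day 4 correlation ρ of 0.3, 0.5 or 0.9 the ratio is 1.54, 1.33 or 1.05. With 3 such subjects in 33, average variance is (30 + 3 × ratio)/33, a rise of 5%, 3% or 0.5%.

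One limit remains. The Retest text in Section 3.5.1 treats a reaction that grows over time as supporting phototoxicity, so a Day 3 score alone may understate it. The change reduces the bias but may not remove it.

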On Day 1, subjects will have an area of skin on their back, approximately 50 cm^2 , divided into 6 equal sites marked with a surgical marker. Each of the sites will be irradiated with full spectrum UV light (UVA/UVB), with each exposure differing from the previous by a factor of 1.25 (ie, each irradiated site will be exposed to a 25% greater dose of UV irradiation than the previous site).²

The areas involved in MED determination will be different from the study product application sites. Evaluation of the exposed sites will be performed on Day $2.^3$

Day 2

On Day 2, a trained evaluator will examine the 6 irradiated sites and determine the MED for each subject. To determine the MED the sites are read and scored by the trained evaluator for the presence of erythema. There will be a main evaluator for the study; a backup evaluator will also be assigned in the event that an emergency occurs and the main evaluator is unable to attend the

study visit. The lowest exposure dose of the 6 irradiated sub-sites showing an erythema response is selected as the minimal erythema dose (see Section 3.5.7 for scoring scale).

The clinical staff will remove the patches approximately 24 (\pm 2) hours after application and evaluate the application sites according to the criteria in Table 3 and Table 4 (Section 3.5.7). Evaluations will be recorded on the appropriate CRF. The timing of the UVA and UVA/UVB irradiation will be calculated based on the output of the solar simulator. The solar simulator output will be measured prior to each irradiation. Details of the UV irradiation including output of the simulator, time of exposure, equipment used, and staff performing irradiations will be documented. The sites designated for irradiation will receive 16 J/cm² of UVA radiation followed by 0.5 times the MED of UVA/UVB irradiation, using a filtered light source (see Section 3.5.4). One additional site (untreated) will be irradiated with 16 J/cm² of UVA radiation followed by 0.5 times the MED of UVA/UVB radiation, using a filtered light source and will serve as an untreated control.

In addition, AEs and concomitant medications will be reviewed and recorded, as appropriate.

Day 3

On Day 3, approximately 24 (± 4) hours after irradiation (ie, approximately 48 (± 4) hours following product application) all application sites and the untreated control site will be evaluated. In addition, AEs and concomitant medications will be reviewed and recorded.

Day 4/End of Study

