4.3.1. Background and Demographic Characteristics

Descriptive statistics will be used to summarize demographic characteristics (age, gender, Fitzpatrick skin type, and race) and background characteristics for the randomized subject population. Past/coexistent medical history information for all randomized subjects will be presented in a by-subject listing.

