4.3.2. Study Product/Visit Compliance

Descriptive statistics will be used to summarize study product compliance for the randomized subject population.

4.4. **Prior and Concomitant Medications**

Prior and concomitant medication information for all randomized subjects will be presented in a by-subject listing.

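### Skin scores are summarised and tested in completers only, so a subject graded after irradiation on Day 3 who misses Day 4 has observed grades left out of every planned score summary

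*Combined protocol and SAP*

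**What the plan says.** Section 4.3 defines the set for the phototoxicity evaluation: "The evaluation of phototoxicity potential of the study products will be assessed for all subjects completing the study". The synopsis, under safety evaluation, says the same. Section 4.6.1 carries the limit into the descriptive tables for Days 2, 3 and 4: "All assigned scores during the study for subjects who complete the study will be summarized using frequency counts by treatment". The ANOVA comparisons in that section use the mean of the Day 3 and Day 4 scores, each the sum of erythema and edema.

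Other outputs use wider sets. For adverse events, "All subjects who receive treatment will be evaluable for AEs". Section 4.3.1 summarises demographics and "background characteristics for the randomized subject population". Section 4.4 states: "Prior and concomitant medication information for all randomized subjects will be presented in a by-subject listing".

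On Day 3, about 24 hours after irradiation, section 3.5.1 requires that "all application sites and the untreated control site will be evaluated"; Day 4 is the end of study. Under section 3.6.6, a patch-area response that fits the "irritation criteria summarized in Table 3 and Table 4 will not be considered an AE". Section 3.3.1 enrols enough subjects "in order to provide 30 completed subjects evaluable for analysis". Section 3.3.4 asks for a final evaluation of a subject who withdraws, where possible, but section 4 does not say how that grading is used.

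**The concern.** The study exists to measure skin response after irradiation, yet that outcome has the narrowest analysis set in section 4. A missing Day 4 score is a reason to leave a subject out of a Day 3/Day 4 mean. It is no reason to remove Day 2 and Day 3 grades already recorded from tables that count grades day by day.

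At stake is the possible omission of an observed reaction from a safety summary. If leaving has nothing to do with the reaction, only information is lost. If a reaction confined to an irradiated product site contributes to leaving, the omission favours a finding of no phototoxicity. If the subject also reacted at the untreated irradiated site or at the non-irradiated product site, the contrasts need not shrink.

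**Working it through.** **Step 1: where could a Day-3-only subject's grade appear?** Take a subject irradiated on Day 2, graded on Day 3 and absent on Day 4.

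- Frequency counts (4.6.1): excluded, completers only.
- ANOVA (4.3, 4.6.1): excluded, completers only.
- AE tables (4.6.2): the subject is in the denominator, but a grade on Table 3 or 4 is not an AE (3.6.1, 3.6.2.1, 3.6.6).
- By-subject listings: section 4 names them for medical history, medications, and deaths and SAEs, but not for skin scores.
- Final evaluation at withdrawal (3.3.4): no use stated in section 4.

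No score summary named in section 4 contains the grade.

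**Step 2: is there a planned figure to reproduce?** No. Section 4.2 rests the 30 evaluable subjects on industry and regulatory convention. It gives no alpha, power, effect size, SD or dropout rate, and the protocol gives no reactor rate, so an expected effect cannot be derived. What follows is conditional on assumed counts.

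**Step 3: one lost reactor, effect on the count.** Assume 30 completers with no reaction and one reactor who leaves after Day 3.

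- As planned: 0/30. One-sided 95% upper limit (Clopper-Pearson) = 1 − 0.05^(1/30) = 9.5%.
- With that subject counted: 1/31 = 3.2%, upper limit 14.4%.

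**Step 4: effect on the mean contrast.** The Retest text in section 3.5.1 requires both erythema and edema before phototoxicity is suspected. On Table 3 such a reaction scores from 1 + 1 = 2 to 3 + 2 = 5. If it is confined to the irradiated CCP-020 site and every other score is 0, the irradiated minus non-irradiated contrast is:

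- completers only: 0/30 = 0
- with the Day 3 score included: 2/31 = 0.065 to 5/31 = 0.161

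**Step 5: effect on a p-value.** The ANOVA model is not specified, so I tried two. Assume k subjects of n react equally at the irradiated CCP-020 site only and all other scores are 0. The size of the score then cancels.

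- One-sample t on the contrast: t = √[k(n−1)/(n−k)], n − 1 df.
- Subject-by-site ANOVA, five sites, pooled error: t = √[5k(n−1)/(2(n−k))], 4(n − 1) df.

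| Reactors | One-sample t: p | Five-site ANOVA: p |
|---|---|---|
| 1 of 30 | 0.326 | 0.117 |
| 2 of 31 | 0.161 | 0.025 |
| 3 of 30 | 0.083 | 0.005 |
| 4 of 31 | 0.043 | 0.001 |

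Adding one lost reactor crosses 0.05 (an assumed threshold, since section 4 states none) between 3 of 30 and 4 of 31 under the first model, and between 1 of 30 and 2 of 31 under the second. With no other reactors, 1 of 31 gives p = 0.325 under the first and 0.116 under the second, so one lost reactor would not by itself reach 0.05 under either.

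**The case against.** The strongest reply is that the exposure is very small. Product is applied once, patches come off and irradiation is given on Day 2, and the study ends on Day 4. The ANOVA loses only someone who is graded on Day 3 and misses one visit about 24 hours later, with no dosing left to avoid. Section 3.3.4 asks for every effort at a final evaluation, and suspected reactors may be retested. This stands, and it keeps the point minor. It does not explain leaving out a grade already taken, and section 4 plans no summary of retest results.

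A second reply is that the endpoint needs both days. This also stands. A Day 3 score alone is not the planned Day 3/Day 4 mean, and the Retest text treats rising intensity as support for phototoxicity, so a delayed reactor who left after Day 3 could enter as a zero. A reader might infer that available-score means should replace the completers ANOVA; the documents do not support going that far.

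A third is that the loss would be visible, and this is right. A reader might infer that a lost subject is replaced and disappears. Section 3.3.1 says only that enough subjects are enrolled to give 30 completers, which fits over-enrolment in advance equally well. Randomized and treated denominators would show 31 against 30 scored, and section 3.3.3 has the reason for leaving sought and recorded on the CRF. What is missing is the grade, not the subject.

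A fourth is that some symptoms would still reach the AE tables. Tables 3 and 4 include itching but not pain or burning, so those could be recorded as AEs. The graded erythema and edema would remain absent.

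Last, section 3.4.5.2 refers to an SAP to be finalised, and no separate SAP is among the documents. It may add a score listing or a wider set. The completers restriction is nonetheless stated affirmatively in the protocol, so a wider set there would contradict the protocol text.

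**Conclusion.** The point holds as a minor, inexpensive correction. The protocol's stated rule omits observed post-irradiation grades of a Day 3 subject who does not complete from every score summary section 4 names, and the AE tables do not carry those grades.

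The size is zero if nobody leaves after Day 3. With one lost reactor and no others, the reactor count is understated as 0/30 instead of 1/31. The number of reactors, the single loss and a reaction confined to one site are all assumptions, and the upper limits illustrate a proportion the plan does not report. The term for completing the study is not defined; I read it as attending Day 4.

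Two stronger inferences are not supported. One is that the rule would change the significance result: that depends on the unspecified model and on how many other reactors there are. The other is that reactors are systematically withdrawn: the protocol treats skin reactions as outcomes to grade and, where warranted, retest. The concern does not need that reading, since any exit after the Day 3 grading, including at the subject's request or the Investigator's discretion, has the same consequence.

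**What to change.** Amend sections 4.3 and 4.6.1 and the matching synopsis text as follows.

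1. Give the Day 2, 3 and 4 frequency counts for every treated subject with a score on that day, with the denominator shown per day.
2. List all skin scores by subject for all treated subjects, with the reason for leaving where a subject did not complete.
3. Keep the completers ANOVA on the Day 3/Day 4 mean. Add a sensitivity ANOVA on all irradiated subjects with at least one Day 3 or Day 4 score, using the mean of the available scores, and note that a Day-3-only value may miss a later increase.

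The aim of 30 completers can stay. The cost is the text changes, one listing and one extra run. The gradings are already scheduled, so no visits, assessments or subjects are added.
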